7.2 Recruitment, Screening, and Randomization Procedure

Prospective study participants include any person with T2D who seeks treatment in the Virta Treatment program. Prospective participants will be identified through screening during a Virta pre-enrollment period. As part of the normal Virta enrollment process, all people complete an online health assessment with a medical provider. People who meet initial study criteria will be approached by a Virta HCP during the routine new-patient visit and further screened for exclusions, such as currently eating a self-reported very-low carbohydrate diet or currently using a personal CGM. Those who continue to meet inclusion/exclusion criteria and who express interest in study participation will be contacted by members of the Virta research team who will explain the study in further detail, complete additional screening questions, answer questions, and obtain informed consent as appropriate.

CGM vs. BGM to Optimize Glycemic Outcomes in T2D Following the Virta Treatment Ver. 2.0 06Dec2022

Up to 2,000 free-living adults with T2D may be invited to participate in this study, and approximately 200 participants will be consented; this is based on the following assumptions 1) approximately 10% of people choose to volunteer to participate in research 2) some participants (estimate up to 50 people) will consent, but may withdraw before being randomized and therefore will need to be replaced and 3) approximately 15% attrition is expected for the randomized participants within the 3-month study intervention period. Therefore, to meet the sample size calculation requirements, 150 qualifying participants need to be randomized to obtain 126 participants with evaluable data. Evaluable data is defined as participants with at least five days of blinded Libre Pro CGM data at baseline.

All participants must obtain Virta's standard medical approval from a Virta HCP and meet all eligibility criteria, as defined in Section 6, to participate in the study. Once the informed consent form (ICF) has been signed, the participant is formally enrolled in the study and a participant ID number will be assigned and recorded in the shared Virta and IDC study database (REDCap). Participants will be randomized 1:1 to either the BGM or CGM arm (Table 1) once a minimum of five days of blinded Libre Pro CGM data is confirmed by the participant. Of note, the blinded Libre Pro CGM system provides a way for the participant to see the number of days of data recording while the sensor is in use. If a participant wears a blinded Libre Pro CGM at baseline that does not capture at least 5 days of data, the participant will be provided the option to wear a repeat blinded CGM or choose to exit the study. Participants who capture five or six days of blinded CGM data may also be provided an option to wear a repeat blinded CGM to collect additional blinded CGM data.

Blinding procedures are not described since blinding is not possible in a study comparing two different methods of glucose monitoring (BGM versus CGM); the participants will know which arm they are assigned to in order to conduct the appropriate monitoring.

Given that enrolling participants takes several months to complete, a block randomization scheme will be used to ensure that participants are assigned to BGM and CGM arms in approximately equal proportions each month. The participant randomization schedule will be generated by the study statistician using the random number generator in SAS. Participants will remain in their assigned study arm throughout the intervention and follow-up period (day 0 to day 194).

Table 1. Randomization arms and associated study-arm devices

Study Arm	Devices Used
Blood Glucose Monitoring (BGM) Arm	Commercially approved FreeStyle Libre Pro Sensor and Reader (blinded CGM) Commercially approved Precision Xtra Blood Glucose & Ketone Monitoring System for glucose and ketone monitoring; used in accordance with package inserts.
Continuous Glucose Monitoring (CGM) Arm	Commercially approved FreeStyle Libre Pro Sensor and Reader (blinded CGM for baseline assessment only) Commercially approved 14-day, personal FreeStyle Libre 2 system and associated phone-based app; used in accordance with package inserts.

	Commercially approved Precision Xtra Blood Glucose & Ketone Monitoring System used for fingerstick ketone monitoring and as indicated for glucose monitoring; used in accordance with package inserts.
--	--

8 Study Intervention

The intervention will compare the impact of two glucose monitoring methods, BGM or CGM, as part of Virta Health's diabetes care program. All care and education are provided via telemedicine (i.e., virtually) and with the use of web-based software applications for biomarker reporting, monitoring, and communication with Virta's care team.

As part of standard Virta Treatment, participants will receive continuous coaching from the Virta care team that focuses on modifying daily nutrition choices to achieve and sustain nutritional ketosis as measured by blood BHB 0.5-3.0 mmol/L. The care team includes health coaches for day-to-day program guidance and HCPs for medication management and clinical oversight. Virta HCPs review glucose values reported by participants in the Virta app. HCPs make proactive and reactive medication dose adjustments to prevent hypoglycemia while participants are experiencing metabolic improvements. Care for Virta participants is provided continuously and is not limited by specific time milestones (e.g., appointments are not at scheduled timepoints).

The current Virta Treatment relies on BGM for glucose assessment and does not supply CGMs as part of routine care. Thus, the intervention under study is use of CGM compared to BGM (Virta's current standard care) for glucose monitoring.

In the BGM arm, participants, health coaches, and Virta HCPs will use BGM and ketone data to guide medication management decisions and to encourage program adherence, per their usual practices. The blinded Libre Pro CGM data collected at baseline and during the intervention and follow-up periods will not be available to participants or the Virta care team; however, data from the blinded Libre Pro CGM assessments can be made available to BGM arm participants after study completion, upon request from the participant. BGM and ketone data will be used to help determine which foods, behaviors, and medications sustain nutritional ketosis. Typical BGM assessment in the Virta Treatment includes one to two fingerstick glucose tests per day depending on the participant's medication regimen. Fingerstick data is reported in the Virta app by the participant.

In the CGM arm, participants receive Virta's usual care except instead of using BGM, participants, health coaches, and Virta HCPs will use real-time and retrospective CGM and ketone data to guide medication management decisions and to encourage program adherence. Emphasis will be placed on guiding participants to use the CGM device and its associated data to determine which foods, behaviors, and medications help them achieve CGM glucose targets and sustain nutritional ketosis. Glucose target ranges will be individualized for each participant and use of CGM alarms to alert participants of high or low glucose will be individualized based on a shared decision-making approach that aligns with current guidance on providing technology-enabled diabetes care. Virta Health coaches will consider CGM data during participant contact as needed, and HCPs will systematically assess CGM data during the defined Contact Periods and at any point throughout the study as indicated by clinical care. IDC will provide minimal participant support for technical CGM-related issues.

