3.1 Background Information

More than 37 million people in the United States have diabetes, and type 2 diabetes (T2D) accounts for 90-95% of all diagnosed cases. The number of adults diagnosed with diabetes has more than doubled in the last 20 years, which creates significant burdens for the economy, healthcare system, and families affected by the disease. Options to help manage T2D are more important than ever before.¹

Nutrition-related interventions have long been recognized as a critical component of diabetes care and management. Current guidance from the American Diabetes Association (ADA) Standards of Medical Care (SOC) states there is no “one-size-fits-all” eating pattern, or ideal macronutrient distribution, that works for all people with diabetes.² A variety of eating patterns (e.g., Mediterranean, very-low-carbohydrate, vegetarian) have demonstrated good efficacy for people with diabetes (PWD). However, evidence suggests all healthy eating patterns should emphasize non-starchy vegetables, minimal added sugars and refined grains, and whole foods over highly processed foods whenever possible. Reducing overall carbohydrate intake has demonstrated the most evidence for improving glycemia in people with T2D and should be considered with emphasis on the aforementioned components of healthy eating pattern.²

People with T2D often learn about how their food choices impact their glucose by performing intermittent fingersticks, which is also called blood glucose monitoring (BGM). Continuous glucose monitoring (CGM), which tracks glucose continually over time is also an option. However, as of 2022, CGM is only recommended in the ADA SOC for PWD who require insulin.

CGM vs. BGM to Optimize Glycemic Outcomes in T2D Following the Virta Treatment Ver. 2.0 06Dec2022

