Several studies in PWD who use insulin suggest that CGM may lead to greater improvements in glycated hemoglobin (HbA1c) compared to usual care, which is often BGM.^{3,4} CGM studies in PWD who do not use insulin are sparse; however, Jackson et al conducted a review of the available data and reported CGM may improve glycemic outcomes in PWD not using insulin and may have the potential to improve lifestyle changes and adherence to diabetes treatments.⁵ Wright and Subramanian, also suggest there is evidence that CGM provides benefits to PWD who are treated with less-intensive therapies; they present data showing that behavioral interventions that use CGM improve dietary habits, physical activity, bodyweight, and problem-solving skills.⁶

One of the key benefits of CGM is the ability to see granular changes in glycemia over time. While HbA1c has long been the gold-standard for assessing glycemia, the HbA1c does not provide a clear picture of glucose variability or the patterns of hyper- and/or hypo-glycemia. The 2022 ADA SOC recognizes that CGM can provide better insights into more personalized diabetes care, and they call out ten core metrics that should be considered when evaluating CGM data. There is specific emphasis on time in range (TIR), the goal of which for most PWD is 70% of time in the target glucose range of 70-180mg/dL.⁷ A 14-day TIR has been shown to correlate well with HbA1c⁸ and emerging data suggest TIR is also correlated with risk of diabetes-related complications.⁹

Two recent randomized controlled trials in PWD who were treated with basal insulin¹⁰ or less intensive therapies¹¹ showed that use of CGM improves TIR by about 15%, which is noteworthy when considering a 5% improvement in TIR is considered clinically meaningful.¹² CGM's immediate feedback on current glucose levels and the retrospective review of glucose patterns from CGM reports may help optimize diabetes therapy, including dietary changes. The value of CGM for making nutrition and lifestyle modifications has strong potential, but it needs further research, which could lead to expanded indications for CGM for people with T2D.

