6.1 Participant Inclusion Criteria

To be eligible to participate in this study, an individual must meet all the following criteria:

1. Age \geq 18 years
2. U.S. residence with plans to remain in the U.S. for study duration (for shipping purposes)
3. Diagnosis of T2D
4. HbA1c between 7.0-11.5% documented within 180 days prior to consent
5. Stable diabetes medication regimen and lifestyle patterns (eating and activity) within approximately 30 days prior to consent
6. Using at least one glucose-lowering medication (oral or injectable) for diabetes management at the time of consent; if using insulin, this may include up to a total of three or fewer insulin injections per day (e.g., once or twice daily basal insulin, once or twice daily basal insulin plus one prandial insulin dose, once or twice daily pre-mix insulin, or another combination etc.)
7. English language comprehension
8. Confirmed download of FreeStyle Libre 2 app on personal smartphone with regular WiFi or cellular data access
9. Willing and able to record study data using smartphone, tablet, and/or computer
10. Willing to wear and use study-provided CGM devices for up to 7 months
11. Willing to perform fingersticks to test blood glucose
12. Willing to perform fingersticks to test blood ketones twice daily
13. Eligible to initiate and intention to participate in the dietary changes required as part of the Virta Treatment for at least 7 months

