15.5 Sample Size Determination

The sample size estimation is based on the following assumptions:

- 80% power (at 0.05 significance level) to test the primary hypothesis, which is the difference in TIR between BGM and CGM arms
- anticipated mean difference in TIR between CGM and BGM = 10%
- anticipated standard deviation of TIR in each arm = 20%

The two-sided t-test suggests N=63 for each arm. Assuming an 85% retention rate at the end of the 3-month Post-Dietary Change period brings the required sample size to approximately N=75 per arm; or N=150 randomized participants with adequate Baseline data.

Consented participants who are not randomized do not count toward the 150 total participants; these participants may be replaced.

16 Ethics/Protection of Human Subjects

This protocol and any amendments will be submitted to Advarra for formal approval of the study conduct. The decision of the IRB concerning the conduct of the study will be made in writing to the Investigator. A copy of the initial IRB approval letter will be provided to the study funder (Abbott Diabetes Care) before commencement of this study.

This study will be conducted in full accordance with all applicable Federal and state laws and regulations including 45 CFR, and the HIPAA Privacy Rule. Any episodes of non-compliance will be documented. The Investigators will perform the study in accordance with this protocol, will obtain consent, and will report unexpected problems in accordance with IRB policies and procedures. Collection, recording, and reporting of data will be accurate and will ensure the privacy, health, and welfare of research participants during and after the study.

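### Insulin users and non-users are pooled with no adjustment for insulin and no pre-specified TIR estimate by baseline insulin use, so the plan gives no separate result for people not using insulin

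*Combined protocol and SAP*

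**What the plan says.** **Eligibility.** Section 6.1 requires at least one glucose-lowering medication and admits insulin users within a limit: "if using insulin, this may include up to a total of three or fewer insulin injections per day". No quota or cap is set for either group.

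**Randomisation.** Section 7.2 says "a block randomization scheme will be used to ensure that participants are assigned to BGM and CGM arms in approximately equal proportions each month". The blocks control balance over calendar time only.

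**Analysis.** The primary model in Section 15.1 contains treatment, period, their interaction and a random patient effect. The models in Section 15.2 likewise have no insulin term. Neither the outcome lists in Section 4.2 nor the exploratory analyses in Section 15.3 include TIR by insulin use. Exploratory outcome 5 describes medication change by class and dose, which is a different question.

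**Background.** Section 3.1 states that "as of 2022, CGM is only recommended in the ADA SOC for PWD who require insulin" and describes CGM studies in people not using insulin as few. It says that further research on CGM for nutrition and lifestyle change is needed, "which could lead to expanded indications for CGM for people with T2D".

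**Stated question.** Section 3.2, the objectives in Section 4.1 and the hypotheses in Section 15.4 concern people with T2D as a whole within the Virta programme. None singles out people not using insulin.

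**The concern.** Section 3.1 separates two groups: people who require insulin, for whom CGM is already recommended, and people who do not use it, for whom evidence is thin. The trial recruits both and plans one pooled difference. A reader who wants to know what the trial shows about non-users will find no pre-specified figure. Any later split by insulin use would be post hoc, with the definition and model chosen after the data are seen.

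There are reasons to want the split. Under Sections 8 and 3.1, glucose data guide medication as well as diet, fingerstick frequency in the BGM arm depends on the medication regimen, and most insulin users in the earlier programme trial had insulin stopped or reduced by 10 weeks. These make a different course by insulin use plausible, though they do not establish one.

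A second, smaller matter is that insulin use is known at consent and may predict TIR change, yet it is used neither in the randomisation nor in the model, so some precision may be given up.

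**Working it through.** **Inputs from Section 15.5.** "80% power (at 0.05 significance level) to test the primary hypothesis"; "anticipated mean difference in TIR between CGM and BGM = 10" percentage points; "anticipated standard deviation of TIR in each arm = 20" percentage points; 85% retention. Section 7.2 gives 126 evaluable participants, or 63 per arm.

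**Assumed, because the documents give no value.** Insulin share p = 20% to 50%; a 10-point difference in TIR change between users and non-users. The SD of 20 is applied to the treatment contrast as in the plan's own t-test, since no within-patient correlation is given for the mixed model.

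**1. The plan's sample size.** n per arm = 2 x (1.96 + 0.842)^2 x 20^2 / 10^2 = 62.8, so 63. This matches "The two-sided t-test suggests N=63 for each arm". Then 63 / 0.85 = 74.1, so 75 per arm and 150 in total. Both figures reproduce. They carry no allowance for an estimate by insulin use.

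**2. Gain from adjusting for insulin.** Variance explained = p(1-p) x 10^2. At p = 40% this is 24 out of 400, leaving a residual SD of sqrt(376) = 19.4.
- Unadjusted 95% half-width: 1.96 x 20 x sqrt(2/63) = 6.98.
- Adjusted: 1.96 x 19.4 x sqrt(2/63) = 6.77.

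So about 7.0 falls to about 6.8. At p = 20% or 50% the adjusted figure is also about 6.8.

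**3. Interval for non-users.** With m = 63(1-p) non-users per arm, half-width = 1.96 x 20 x sqrt(2/m).

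| Insulin users | m per arm | 95% half-width (points) |
|---|---|---|
| 20% | 50.4 | 7.8 |
| 40% | 37.8 | 9.0 |
| 50% | 31.5 | 9.9 |

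**4. Why no test is proposed.** With a true 10-point effect in non-users, power in that stratum is Phi(10/SE - 1.96), where SE = 20 x sqrt(2/m). This is 71% at 20% users (SE 3.98) and 51% at 50% users (SE 5.04). For a 10-point difference in effect between strata, SE = 20 x sqrt(2/m + 2/(63-m)), which is 8.91 at 20% users and 7.13 at 50%. Power is then 20% and 29%.

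**5. Chance imbalance without stratification.** The SD of the between-arm difference in insulin share is sqrt(2p(1-p)/75): 6.5 percentage points at p = 20%, 8.0 at 40% and 8.2 at 50%. A gap of 10 percentage points or more has probability 13% at p = 20% and 22% at p = 50%. At p = 40%, the 95% limit for its effect on the primary contrast is 1.96 x 0.080 x 10 = 1.6 TIR points.

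**The case against.** The strongest reply is that the trial never set out to estimate an effect in non-users. Its question is CGM versus BGM within a nutrition programme for T2D, and the pooled analysis answers it. The study describes itself as non-pivotal, and the remark about wider indications is a possibility, not a planned claim. This stands, and it is why the point is a suggestion. A stratum estimate would also be imprecise, which stands too.

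Three stronger readings are tempting, and the documents do not support them.

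- **That the trial cannot inform on non-users.** They are enrolled and randomised, and medication class and dose are recorded at baseline (Section 4.2.3 and Appendix B). A non-user estimate can be produced; it is only not pre-specified. The lack of stratification does not prevent it.
- **That a positive pooled result would probably come from insulin users.** The smallest significant pooled difference is 1.979 x 20 x sqrt(2/63) = 7.05 points. With no effect in non-users, users would need 7.05/p: 14.1 points at 50% users, 23.5 at 30% and 35.3 at 20%. This is arithmetically possible at a high insulin share, but nothing in the protocol points to it. Section 3.1 reports a TIR gain of about 15% from trials in both basal-insulin and less intensively treated patients. The earlier programme trial reports medication reduction for sulfonylureas (93%) as well as insulin (87%), so de-escalation is not peculiar to insulin.
- **That unstratified randomisation biases the result.** It does not. The 1.6 points in step 5 is random variation already covered by the standard error, and the planned SD of 20 is given for each arm as a whole.

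**Conclusion.** The point holds as a gap in pre-specification. The pooled TIR comparison is valid for the stated T2D-wide question. The plan nevertheless offers no separate pre-specified estimate for people not using insulin, whom its own background identifies as the under-studied group.

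The gain on offer is modest: roughly 0.2 points off the primary half-width, and a non-user interval of about +/-8 to 10 points. These figures rest on an assumed insulin share of 20-50%, an assumed 10-point difference in TIR change by insulin use (for the precision gain), and the plan's SD of 20. The concern shrinks as the share of non-users rises, because the pooled result then increasingly describes them. This is something to consider, not a required correction.

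**What to change.** - **Section 7.2, only if enrolment has not started:** stratify the block list by insulin use at consent (yes/no). If enrolment has begun, leave the list alone and make the analysis changes only.
- **Section 15.1, primary model:** add baseline insulin use and insulin-by-period as fixed effects.
- **Section 15, supportive descriptive analysis:** fit a model that also includes the treatment-by-period-by-baseline-insulin term, with its lower-order terms. Report the CGM-minus-BGM difference in TIR change with a 95% CI in each stratum, without a separate test. The three-way term is needed because the two terms added to the primary model do not by themselves give within-stratum treatment differences. Define strata by baseline status, since medication changes during follow-up.
- **Reporting:** base any conclusion about non-users on that stratum estimate.

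The cost is a two-level randomisation list and a few lines of analysis text, with no new patients or data. The downside is that the non-user interval is wider than the overall one and will not settle the question alone.

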8.1 Ongoing Study Procedures

Study duration is expected to be approximately 215 days, an approximately 21-day baseline assessment period plus a 194-day Post-Dietary Change intervention and Follow-Up period. Throughout the study, participant communication with Virta staff will occur via phone, secured email, and chat messages within the Virta app, which feed into the Virta electronic medical record (EMR).

